Evaluation of Wear Experience with Water Surface Toric Contact lenses
on long lens-wear days

NCT 04844281

Evaluation of Wear Experience with PRECISION1® Toric Contact lenses

on long lens-wear days

[name], OD MS

The Ohio State University College of Optometry
Innovation in Vision and Eye care Research Group - iVERG

Purpose

The purpose of this study is to explore the performance of PRECISION1® Toric lenses on long days of lens wear.

Study Overview

This open-label study is of current soft contact lens wearers who wear their contact lenses for longer than a typical workday. Participants who regularly wear contact lenses for long days will be fit into PRECISION1® Toric contact lenses. Participants will be assessed after 1-2 weeks of wear with a follow up visit (Visit 2) to ensure a successful lens fit. Refitting will occur if necessary. After final completion of Visit 2, the five survey days will be determined. On 5 days between Visit 2 and Visit 3, the participant will respond to a survey sent to their smart phone to report the time they insert their lenses each morning. Each evening, the participant will be sent a survey for immediate response about their current comfort and vision with lens wear. The surveys will be sent at 10, 12, 14 and 16 hours of lens wear. Participants will return for a final follow-up visit including a VAS survey and the CLDEQ8 survey of their lens wear experience.

Background

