Soft daily wear contact lenses are used by an estimated 40.9 million adults in the United States.¹ Contact lenses which are worn for daily wear are considered minimal risk by the FDA, and risks to wearers are minimized by proper lens care and hygiene. Daily disposable contact lenses do not require daily cleaning and overnight storage, which lessens the required amount of time to care for contact lenses. In addition, daily disposable contact lenses are associated with less lens deposits, which decreases associated comfort issues in lens wearers, including decreasing the risk of triggering Giant papillary conjunctivitis (GPC) and/or ocular allergic responses in patients.² Additionally, daily disposable contact lens wearers are not likely to expose their lenses to water and tend to have better lens hygiene since these lenses do not require daily cleaning. This is reflected in a study which found less superficial punctate staining and symptoms of dryness when comparing daily disposable contact lens wear with planned replacement lenses.³ The subjects in this study will be fit into PRECISION1 toric daily disposable contact lenses, which are less likely to be associated with the already minimal risks of daily contact lens wear. Because of these benefits of

daily disposable lenses, and the accompanying improvement in comfort, it is likely that these lenses will provide long lasting comfort and vision throughout the day. As many people wish to wear their contact lenses to work and then throughout the evening, it is of interest to know how a lens performs over the course of a day into evening.

Key Endpoints:

- Subjective assessment of comfort and vision at time points of extended contact lens wear (Scale of 1 -10) at evening time points on 5 days.
- Visual Analog Scale survey of lens wear symptoms (comfort, dryness, vision) at study end.

Study Time Points:

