Final visit: The contact lens follow up visit will occur approximately 1 week (± 5 days) following the follow up visit. Subjects will have visual acuity, an assessment of ocular health. Subjects will then complete surveys about their lens wear experience.

Evening Surveys will include 1-10 forced choice grading of comfort and vision.

End of study surveys will include a lens experience survey, the CLDEQ-8 survey, and VAS scales assessing:

Overall Quality of vision
End of Day Quality of vision
Overall comfort
End of Day comfort
Overall dryness
End of Day dryness

Recruitment

Potential subjects may see posters placed on bulletin boards at The Ohio State University or local eye care offices, emails to students, faculty and staff at OSU, online or paper ads, or signs on the OSU buses. A search of the electronic medical records of The Ohio State College of Optometry may be done to identify possible subjects who then may be contacted by email or phone with information about the study. Word of mouth referrals by study team members to OSU employees and friends may occur. Emails to alumni of the OSU College of Optometry may be sent for local doctors to notify eligible potential subjects about the study.

Inclusion criteria:

- Ages 18-40
- Subjects must be current soft toric contact lens wearers with longs days of lens wear within the parameters of P1 lenses available.
- Subjects must have 20/25 or better distance visual acuity with current lenses.
- Subjects should have had an eye exam in the past two years (self report).
- Good general health (defined by medication use that has not changed within the last month and the absence of medical conditions or treatments that are deemed confounding to the data as determined by the PI).
- Ability to give informed consent.
- Subjects must have a working smart phone or device and be willing to receive and respond to texts and or emails.
- Willing to spend time for the study. Subjects will be required to attend three study visits (with a possible fourth visit if needed), wear contact lenses on days between study visits, and must respond to communications on a smart phone or other electronic device on 5 weekdays between visits 2 and 3.
- Either gender.
- Any racial or ethnic origin.

Exclusion criteria:

- No current ocular inflammation or infection as assessed by the study investigator.
- Females who are currently pregnant or lactating or plan to become pregnant during the course of the study.

Consent and Confidentiality

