A team member trained in the consent process will provide the consent document for the potential subject to read and will review the procedures with reference to the consent form. The individual is then provided with time to read the consent form and offered the opportunity to ask questions. The participant is explicitly told that they may stop participation at any time. All subjects will have the capacity to give informed consent. If there is any doubt as to the subject's ability to consent to the study, the subject will be excluded from the study. If the subject agrees to take part in the screening or measurement, he or she will sign and date the most recent IRB-stamped consent as will the team member. The subject will be provided with a copy of the consent form.

The investigator team is trained in privacy issues and will be reminded of the importance of patient privacy prior to study initiation. Potential study participants will contact us after seeing advertisements, emails or hearing about the study by word of mouth, giving them the choice of whether or not they wish to participate in a study for people with dry eyes. Privacy is protected by limiting information related to study recruitment only, and no other personal or medical information that should be private to the patients. The PHI needed is only for the purposes of this study. It is highly unlikely, indeed extremely remote that the dry eye symptoms or signs are related to private or personal information that should or would be preferred to be kept confidential to the patients. Risk factors for dry eye rarely relate to matters or conditions that would be personal to the patient such as personal relationships, behaviors or diseases that one prefers to keep private and confidential.

Statistical Analysis and Power Calculation

This small sample size was chosen for convenience as this study as enrollment for evening participation may be difficult.

Data Management and Security

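### Study team members may refer friends into an open-label, single-product study with self-rated key endpoints, and the protocol neither excludes people tied to the team nor provides for recording the tie

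*Protocol*

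**What the plan says.** The Recruitment section lists posters, emails to university students, faculty and staff, online and paper ads, bus signs, a medical record search and emails to alumni. It also permits referral by the team itself: "Word of mouth referrals by study team members to OSU employees and friends may occur". The sentence does not say whose friends are meant; the natural reading is friends of the team members. Consent and Confidentiality mentions word of mouth again, with the participant making the contact: "Potential study participants will contact us after seeing advertisements, emails or hearing about the study by word of mouth".

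The Exclusion criteria have two items. One concerns ocular inflammation or infection; the other is "Females who are currently pregnant or lactating or plan to become pregnant during the course of the study". Neither concerns a relationship to the team.

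On design, the Study Overview says "This open-label study is of current soft contact lens wearers who wear their contact lenses for longer than a typical workday" and "Participants who regularly wear contact lenses for long days will be fit into PRECISION1® Toric contact lenses". No second lens, control group or randomisation is described. The first key endpoint is "Subjective assessment of comfort and vision at time points of extended contact lens wear", on a 1-10 scale. The second is a VAS survey of comfort, dryness and vision at study end. Visual acuity and ocular health are assessed at visits but are not key endpoints.

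**The concern.** A friend, relative, student or supervisee of someone on the team may rate the team's study lens more kindly than a stranger would. In a randomised comparison, such goodwill would be spread over both arms and would tend to cancel in the difference. Here there is one arm, every subject knows the product, and no key endpoint is measured independently of the subject's opinion. The extra goodwill goes into the reported level of comfort, vision and dryness. The protocol describes the sample as small and chosen for convenience, so a few tied subjects could carry noticeable weight.

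Who may enrol, how they are found and what is asked at Visit 1 are protocol matters. A statistical analysis plan (SAP) could specify an analysis by recruitment route only if the route had been collected.

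**Working it through.** The protocol gives no sample size, power or expected rating, so there is no figure of its own to reproduce. The check is a reading of the sections together, followed by an illustration with assumed inputs.

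**1. Is the route open, and is there a barrier?** Recruitment permits referral of friends by the team. The Inclusion criteria cover age, lens type, acuity, health and willingness; the two Exclusion criteria cover eye inflammation and pregnancy. A team member's friend who meets these is eligible, as is someone the team teaches or supervises who answers a general university email.

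**2. Is a tie recorded?** The protocol does not say so, and does not rule it out. Data Management and Security describes electronic files of potential and enrolled subjects with contact details, where a referral source could be held. The same section says electronic data files containing protected health information are to be destroyed when the study ends. If the source were held only there, it might not survive for analysis.

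**3. Effect on a mean level.** Let f be the share of tied subjects and d their mean extra inflation in points. Neither is in the documents.

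Bias in the mean = f × d

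| f (assumed) | d (assumed) | Bias in points |
|---|---|---|
| 20% | 0.5 | 0.2 × 0.5 = 0.1 |
| 50% | 1.0 | 0.5 × 1.0 = 0.5 |
| 10% | 0.5 | 0.1 × 0.5 = 0.05 |
| 50% | 2.0 | 0.5 × 2.0 = 1.0 |

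The first two rows span a moderate range, the last two a wider one. Both are illustrations on the 1-10 scale. The same formula applies to the VAS in its own units.

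**4. Effect on change over the day.** The evening ratings are taken at 10, 12, 14 and 16 hours. If tied subjects add d10 at 10 hours and d16 at 16 hours, then

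Bias in the 10-to-16-hour change = f × (d16 − d10)

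With a constant shift, d16 = d10 and the bias is zero. It is not zero if goodwill grows as comfort falls. For example, f = 50%, d10 = 0.5 and d16 = 1.0 gives 0.5 × 0.5 = 0.25 point. A ceiling at 10 would also prevent exact cancellation. So the levels, including the single end-of-study VAS, are fully exposed, and the within-person change much less so.

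**5. What a record would allow.** If ties were recorded, the mean without tied subjects would be free of the f × d term. Its standard error would rise by a factor of 1/√(1 − f), for equal variances: 1/√0.8 = 1.12 at f = 20%, and 1/√0.5 = 1.41 at f = 50%.

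**The case against.** The strongest case against the point has five parts.

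- **The route is ordinary and one of several.** Nothing suggests that team referral will dominate. This stands, and it is why no size can be claimed. It does not explain why friends need to be included at all.
- **Most of the bias is not due to recruitment.** Open label and a known product affect every subject's rating. This stands: excluding tied subjects removes only their extra inflation, and the general limitation of an uncontrolled design remains.
- **The study is exploratory and follows ratings through the evening.** A constant shift drops out of within-person change, as shown above. This stands for the time course, but not for the absolute levels or the VAS.
- **Evening surveys go to the subject's own device.** This lessens face-to-face pressure for those ratings. The VAS, however, belongs to the final visit, and the protocol does not say that the team will not see a subject's answers.
- **The direction is assumed.** Wearers with optometric training could be more critical. That is fair for professional knowledge; it is weaker for personal friendship.

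A reader might also infer three stronger things that the documents do not support. The first is that favourable ratings can never be separated out: the protocol is silent on recording the route, so a record could still be made. The second is that the referral sentence means close colleagues: university employees at large need have no connection with the team. The third is that all College of Optometry staff and students should be barred: the protocol warns that enrolment for evening participation may be difficult, and most such people need have no direct tie to the team.

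**Conclusion.** The point holds as an inexpensive improvement to the design. The protocol expressly allows team members to bring friends into a study with no blinding, no comparator and only self-rated key endpoints. It sets no exclusion for personal or supervisory ties and does not provide for recording them. As written, it secures no way to check whether such ties raised the ratings.

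The exposure lies in absolute rating levels. Its size is unknown. The 0.1-0.5 point range, or 0.05-1.0 point under wider assumptions, rests wholly on assumed shares and assumed inflation, and on tied subjects rating upward. The lower end would be unimportant. The documents state no threshold against which the upper end could be judged.

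**What to change.** 1. In Recruitment, strike 'and friends' from the word-of-mouth sentence.
2. In Exclusion criteria, add study team members, their family and close friends, and anyone they directly supervise or teach. Do not extend this to all College of Optometry staff and students.
3. Record the recruitment route and any remaining tie to the team on a retained Visit 1 data form, not only in the contact file.
4. If any tied subjects are enrolled despite the exclusion, or were enrolled before it took effect, report both key endpoints with and without them.

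The cost is one eligibility line, one form field and the loss of a few easily reached candidates. Posters, ads, bus signs, the record search, general emails and alumni emails all remain. So does word of mouth to university employees who have no such tie.

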Visit 1 will be conducted to consent the subject and determine eligibility. Consenting will be conducted via phone call and REDCap and will occur before the subject arrives on site if possible. After consenting, the visit will begin with visual acuity and an evaluation of the subject's ocular health will occur to determine eligibility including positively responding to the question, "Do you currently wear contact lenses over a long day?" This will ensure that subjects are able and willing to participate in the study since long contact lens wear will be needed. Subjects will be asked their normal morning time for inserting lenses and evening time for lens removal. Eligible subjects can be habitual wearers of soft toric contact lenses and will be fit into PRECISION1®Toric Contact Lenses at this visit and will have a fit assessment and over-refraction completed in order to obtain the best fit and vision. Surveys of impressions of lenses will be completed. For any participant who is an existing PRECISION1® Toric wearer, the lenses will be evaluated and the prescription will be refined if necessary. Any existing PRECISION1® Toric wearer who does not require any changes in prescription at Visit 1 can immediately advance to Visit 2. Otherwise, all participants deemed eligible will be dispensed study lenses and Visit 2 will be scheduled.

Visit 2: Precision 1 Toric follow-up visit will occur approximately 1 week (± 5 days) following Visit 1. Visual acuity and contact lenses fit assessment and over-refraction will be completed. If changes to the lens are necessary, those changes will be made and an additional follow up visit will be scheduled. Subjects will be asked their normal morning time for inserting lenses and evening time for lens removal. Subjects who are new to PRECISION1® Contact Lenses will be dispensed additional lenses to wear until Visit 3.

Five evening survey days: On the morning of each survey study day, the participant will respond to a survey with the time when they inserted their contact lenses that day.. Participants will later be deployed a brief survey at 10, 12, 14 and 16 hours of lens wear that day via REDCap. The surveys will be deployed electronically on 5 days between Visit 2 and Visit 3 that are determined at the time of Visit 2. Every attempt will be made to complete the surveys on business days if possible.

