Subjects who, after study team member coaching, are not able to provide analyzable data may be dismissed from the study. Analyzable data is, for example, that which is obtained for the entire measurement interval and provides a readable eye image. Data may not be analyzable if patient isn't able to stand or move freely to utilize the equipment, to name just two causes issues. These issues are usually revealed at the screening assessment visit. Subjects who cannot provide analyzable data will be dismissed for the study. Subjects who do not keep scheduled visits within the required time frame will be dismissed from the study. Study team members will make reasonable efforts to accommodate subjects' schedules.

Protocol Violations, Discontinuation

In the event that a member of the study team or a representative of sponsor becomes aware of a major protocol violation, the IRB shall be notified within 10 working days.

References

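### The Subject Dismissal rule describes imaging and equipment that this trial does not use, is both discretionary and mandatory, and could cost a dismissed subject the final visit

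*Protocol*

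**What the plan says.** The Subject Dismissal section of the protocol opens with a discretionary rule: "Subjects who, after study team member coaching, are not able to provide analyzable data may be dismissed from the study". It then explains the term by example: "Analyzable data is, for example, that which is obtained for the entire measurement interval and provides a readable eye image". A further example of failure is a patient who is not "able to stand or move freely to utilize the equipment". On timing it says: "These issues are usually revealed at the screening assessment visit". Next comes a second rule for the same condition, this time mandatory: "Subjects who cannot provide analyzable data will be dismissed for the study". A separate rule in the section covers visits missed or kept outside their window. That rule is usable and is not questioned here.

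The evening data are described under Study Time Points: "Participants will later be deployed a brief survey at 10, 12, 14 and 16 hours of lens wear that day via REDCap". On timing: "The surveys will be deployed electronically on 5 days between Visit 2 and Visit 3 that are determined at the time of Visit 2". Each survey asks for a comfort grade and a vision grade from 1 to 10. The final visit collects acuity, ocular health, the lens-experience survey, the CLDEQ-8 and the VAS scales. The Study Overview states in general terms that participants come back for that visit.

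**The concern.** A dismissal rule decides who remains in the study to be measured. This one gives the team a mandatory instruction without a criterion that fits the trial's main data. Staff must either ignore it or improvise, and decisions could then differ between subjects.

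What is at stake is the final visit. It is the only source of the second key endpoint, the end-of-study VAS for comfort, dryness and vision. If a subject were dismissed for incomplete evening surveys, and the surveys were incomplete because the lenses had become uncomfortable, the ratings of those who remain would tend to look too favourable. No later analysis can recover a visit that did not take place. Dismissal and retention are matters of study conduct, so this is not a gap that a statistical analysis plan would normally fill.

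**Working it through.** The check compares the dismissal text with the procedures in the Study Overview, Key Endpoints, Study Time Points and Final visit text. The protocol gives no figure on this point to reproduce.

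**1. Examples against procedures**

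| Subject Dismissal text | Counterpart in this trial |
|---|---|
| Readable eye image | None described. Visits cover acuity, lens fit, over-refraction, ocular health and surveys |
| Entire measurement interval | Term not defined and not used elsewhere |
| Standing or moving to use equipment | No such measurement described |
| Problems seen at screening | Evening surveys start only after Visit 2, so screening cannot reveal a problem with them |

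The text reads as carried over from another kind of study. Consent and Confidentiality has a similar remnant, which speaks of "giving them the choice of whether or not they wish to participate in a study for people with dry eyes", whereas the eligibility criteria call for toric soft-lens wearers with long wearing days and contain no dry-eye criterion either way. That remnant is privacy wording and has no bearing on dismissal; it only supports the view that text was reused.

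**2. Discretionary or mandatory.** Subjects who, after study team member coaching, are not able to provide analyzable data may be dismissed from the study and Subjects who cannot provide analyzable data will be dismissed for the study address the same condition. One allows dismissal after coaching; the other requires it and does not mention coaching.

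**3. Can the rule reach survey data?** Yes. The definition is introduced as an example, so it is not exhaustive. The eligibility criteria also require subjects to answer electronic messages on five weekdays. A team member could reasonably treat a poor survey record as non-analyzable data.

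**4. Amount of evening data per subject**

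- Surveys: 5 days × 4 prompts = 20.
- Ratings: 20 surveys × 2 grades = 40.

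An incomplete record can still hold much of this. A subject who takes the lenses out between 14 and 16 hours on every survey day can answer 5 × 3 = 15 of the 20 surveys. Incompleteness also need not mean symptoms: with insertion at 07:00 (an assumed time), the 16-hour prompt falls at 23:00. How many surveys are enough for analysis is a matter for the SAP and is not part of this point.

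**5. What is lost if dismissal comes before the final visit**

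- All 6 VAS items: overall and end-of-day vision, comfort and dryness.
- The CLDEQ-8.
- The ocular-health assessment. Visit 1 has one; Visit 2 lists only acuity, lens fit and over-refraction; the next one described is at the final visit.

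No sentence asks a dismissed subject to attend that visit.

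**The case against.** The strongest reply is that the text is harmless. Its wording points to an instrument measurement, so a rule about readable images and equipment would remove nobody in a survey study. It can also be argued that the mandatory sentence, which directly follows the remark about screening, applies only at screening, while discretion applies later. Subjects are selected for long wearing days, and their usual insertion and removal times are asked at Visits 1 and 2, so habitual early removal should be less common.

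Much of this stands. A reader might infer that subjects who remove their lenses before 16 hours fail the entire-interval test and must be dismissed. The protocol does not say so: it never calls the 10-to-16-hour window a measurement interval, and this is not the most natural reading. A reader might also infer that early removers are left out of the final visit. That is not supported either, because the Study Overview expects participants to return and the final visit is not made conditional on 16 hours of wear. Only dismissed subjects are left unaddressed.

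The reply does not remove the point. The mandatory sentence is not limited to screening, the open-ended definition does not confine it to images, and it is one of only two stated grounds for dismissal. Selecting long-day wearers reduces early removal but does not exclude it, since no minimum number of wearing hours is set.

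**Conclusion.** The point holds as a minor one. The Subject Dismissal section uses examples that match nothing in this trial, states one rule in two incompatible strengths, and leaves open the removal of a subject for incomplete survey data before the visit that supplies the VAS endpoint.

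The mismatch and the conflict between the two sentences follow directly from the text. The consequence is conditional. It requires that someone applies the rule to survey data, and an upward bias further requires that those dismissed have poorer comfort or vision than those kept. The protocol gives no sample size, early-removal rate or dismissal rate, so no bias figure can be claimed. A reader might conclude that the comfort results will be inflated; the document does not support that.

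**What to change.** Rewrite the one paragraph:

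- Delete the eye-image, equipment and screening sentences.
- Replace the two conflicting sentences with one: a subject may be dismissed for persistent non-response to the surveys after coaching.
- State that taking the lenses out before 16 hours is not a ground for dismissal, and record the time and reason in the evening survey.
- Ask any subject who stops wear, or is dismissed under this rule, to attend the already scheduled final visit for ocular health, VAS and CLDEQ-8.

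The missed-visit rule stays as it is. The cost is one rewritten paragraph and one added survey item; no new visit or committee is needed. The late-hour ratings of early removers remain incomplete, and the analysis has to deal with that.
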